3.3.5 Randomization

Randomization of study patients will be done in equal proportion to Arm I (SIMRT) and Arm II (HTIMRT) using a permuted block design stratified by baseline PSA (<10 v 10 to ≤100), Gleason score (6-7 v 8-10), and short term androgen deprivation therapy (Y v N). The pre-study Gleason score, not that determined by post-MRI biopsy will be used in determining a patient's

stratum; however, patients will not be randomized until after the fiducial markers and prostate biopsies (if elected by the patient) have been performed. Patients whose Gleason score comes back higher and in whom the use or length of androgen deprivation becomes an issue, will then have the opportunity to withdraw from the study without creating potential imbalances. The ability for the patients to withdraw at any time will be described from outset. Based on prior experience, the proportion of patients that withdraw before treatment is about 1-2%. In this trial, the potential for withdrawal is estimated to be 2-3 times higher because of anticipated upgrading (higher Gleason scores in the post MRI biopsies).

Randomization lists for each stratum will be prepared by SCCC Biostatistics prior to the first patient enrollment and provided to the SCCC CRS office where they will be maintained independent of the study team. Members of the study team, including those responsible for patient enrollment, will not have access to the randomization lists.

After informed consent is signed; eligibility is confirmed, a determination has been made regarding optional STAD, the fiducial markers placed and, if elected, prostate biopsies performed, a member of the study team will randomize the subject as per CRS guidelines. The randomization should occur within two weeks after the fiducial marker placement, if applicable or after enrollment.

The nature of study treatment (40 SIMRT vs. 38 HTIMRT treatments) requires that the patients know their treatment. With respect to the collection, processing and analysis of study data, including that deriving from tissue and blood samples, only published data will be available to the patients.

4.0 TREATMENT PLAN

4.1 Pre-enrollment

Multiparametric

Functional-MRI

The block-chart shown in **Figure 2** illustrates the sequence that patients will go through to be evaluated for eligibility, enrolled and randomized. There are two MRI's that will be obtained. The first functional MRI exam of the pelvis and prostate is per standard routine at the University of Miami as part of external beam radiotherapy planning. T2, T1 non-contrast, T1 DCE and DWI MRI scans of the pelvis and prostate at 2.5 mm cuts are routinely performed; when possible (the standard exclusions for MRI with contrast apply). MRI exclusions include

ferromagnetic metal in body/eye, pacemaker, defibrillator, other mechanical device, or extreme claustrophobia (medication with anti-anxiety agents, such as Ativan, may be attempted). Since the DCE-MRI scan involves the use of gadolinium, renal function is assessed to ensure it is adequate, as part of routine management. Again, this is routine clinical practice in our department and will be done prior to enrollment; the procedure is not part of this protocol, but the results are considered for eligibility.

An enema is administered within 2.0 hr. prior to all of the MRI and CT imaging studies to empty the bowel. A diet designed to reduce bowel gas is recommended to begin the day before

[figure not shown]

Figure 2. Block-chart for the HEIGHT trial.

the diagnostic/planning DCE-MRI and before the post-fiducial MRI- and CT-simulation scans described below. The patient is instructed not to fully void before the scans, to mimic bladder position during treatment. The DCE-MRI scans include pre-contrast images and post-contrast images at approximately 30-40 sec intervals, for a minimum of 10 post-contrast scans. We also routinely acquire DWI imaging and plan to routinely acquire MRS when the new MRI install in the department of radiation oncology is complete.

4.2 Assessment of Protocol Eligibility and Enrollment

Patients who have an enhancing lesion (or lesions) with early contrast washin and eventual washout will be eligible if the volume sum of the lesion(s) is <33% of the prostate volume. This will be determined by contouring of the enhancing regions, with consideration of areas water restriction for anterior lesions. Semi-automated software has been developed to assist in this process, which may be used to assist in this evaluation. Eligible patients will be screened by the treating physicians and dedicated protocol nursing staff for fulfillment of eligibility criteria. If the patient is deemed a candidate, protocol consent will then be obtained. If all eligibility requirements are met, the patient will be enrolled. As outlined in **Figure 2**, enrollment occurs prior to fiducial marker placement and optional pretreatment prostate biopsies. ***Randomization occurs after fiducial marker placement, if applicable*** and the review any biopsies done at that time. The patient will be entered into the Radiation Oncology Prostate Cancer Database for data collection and interpretation.

4.3 Prostate Biopsy and Gold Seed Fiducial Marker Placement

Pre-treatment protocol prostate biopsies (optional), when done, and gold seed fiducial marker placement will be performed in a single setting/procedure, if applicable. As per the discretion of the urologist, antibiotic treatment before, during and after fiducial marker placement may be administered. Also prior to fiducial marker implantation/biopsy collection, antibiotic prophylaxis will be prescribed (e.g., Levaquin 500 mg daily, Ciprofloxacin 500 mg twice daily, or a similar antibiotic depending on allergy history and physician preference), may be prescribed/administered.

Pre-treatment transrectal prostate ultrasound-guided biopsies, when done, will be performed using the Eigen Artemis® system when available. The Eigen Artemis system fusion software (FDA approved) may be used to fine-tune the location of the tumor and biopsies by fusion of the previously obtained multiparametric MRI to the transrectal ultrasound in real time. The ultrasound is the true guidance imaging parameter that identifies the prostate boundaries and other nearby structures. The MRI is fused to the ultrasound such that the biopsies may be directed to a region in the ultrasound space. This system, is also described in sections 1.2 and 3.3.4.

No more than 14 needle core biopsies will be obtained. The number and location of the biopsies will be at the discretion of the Urologist performing the biopsies (with input from the PI and protocol team). Ideally, 2-4 of the biopsies will be from the tumor area(s), with a typical arrangement including the left lateral base (LLB), left lateral mid (LLM), left lateral apex (LLA), left medial base (LMB), left medial mid (LMM), left medial apex (LMA), right lateral base (RLB), right lateral mid (RLM), right lateral apex (RLA), right medial base (RMB), right medial mid (RMM) and right medial apex (RMA). During the course of the procedure, hemorrhage may be visualized within the bladder following needle biopsy. If this is the case, or if gross blood is noted at the urethral meatus, bladder catheterization and clot irrigation may be indicated, as determined by the urologist.

The procedure will be performed by a urologist in the Department of Urology at University of Miami Miller School of Medicine. The biopsies will be paraffin embedded in pathology per routine procedures. A pathology reading of the material will be rendered and the remaining blocks will be stored for biomarker analyses. During the same procedure, four gold

fiducial markers will be implanted in the prostate gland, two in the superior region (bilateral bases), two in the inferior region (bilateral apices), laterally arranged. Optimally, the four fiducials should be placed 2 cm from each other and the triangulation should be at least 15 degrees.

4.4 Prostate Cancer Upgrading and Change of Treatment

In the event that the pre-treatment prostate biopsies result in cancer upgrading (higher Gleason score), the treating physician will discuss the appropriate treatment options with the patient. If the Gleason score, on the ultrasound-guided biopsies at the time of fiducial marker placement is higher, the patient must agree to be randomized and treated in accordance with the initial treatment plan, based on the pathologic parameters in the original diagnostic prostate biopsies and not the protocol prostate biopsies.

4.5 Prostate Biopsy Tissue Handling

Immediately following each biopsy core, the tissues will be fixed in 10% formalin per routine. The formalin fixed tissues will be delivered to the Department of Pathology for paraffin embedding and sectioning. The biopsies are to be placed in the tissue processor and processed routinely, and embedded in paraffin. Scheduling of the biopsies on Monday-Thursday is preferred so that the samples will be processed more quickly. Biopsies will be reviewed by a pathologist and the results (Gleason scoring and percent of tumor tissue) recorded in the patient's record per routine. The remainder of the block will be stored per institutional policy in the Department of Pathology and requests for the biomarker analyses made at a time batched staining is possible (after a number of cases have been accrued).

When the tissue is sectioned for biomarker analyses, the slides will be labeled with a research ID number and will not contain patient information. Biomarker data will be entered into the Radiation Oncology Prostate Database which links the patient Medical Record number to a participant's Research ID number and in which data on each patient related to biopsies and treatments will be recorded.

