8.0 CORRELATIVE/SPECIAL STUDIES

Prior to treatment during fiducial marker placement, needle biopsy of the prostate will be performed if the patient agrees (optional). Tissue from paraffin blocks will be used for biomarker quantification and correlative studies with treatment outcome.

At 2-2.5 years after completion of treatment (radiotherapy or androgen deprivation – whichever is longer) all patients, with or without documented failure will undergo transrectal needle biopsy of the prostate, unless clinically contraindicated or the patient refuses. For this biopsy procedure, 12-14 biopsies are recommended with cores taken from sextant regions plus the bilateral lateral base, bilateral lateral mid-prostate, and bilateral lateral apex. At least 2-3 of these biopsies should be from suspicious/Previously positive areas. The bilateral transition zone may be biopsied as well. Fewer biopsies may be obtained at the discretion of the urologist. The ultrasound is the true guidance imaging parameter that identifies the prostate boundaries and other nearby structures. The MRI is fused to the ultrasound such that the biopsies may be directed to a region in the ultrasound space. These data will enable us to evaluate the extent of disease eradication, as well as the prognostic significance of positive biopsies in men who are otherwise free of evidence of disease (low PSA and palpably normal prostate gland).

The 2 yr. post-treatment biopsy is for research purposes. If the biopsies contain prostate tumor cells, the results will be discussed with the patient and additional management considerations made apart from this clinical trial. Many times tumor cells are seen on prostate biopsies at 2-2.5 yr., but the cells show radiation treatment effect. In this situation, it is reasonable to continue to follow the PSA and re-biopsy a year later to look for clearance of the tumor cells. The strategy to re-biopsy will be up to the treating physician and will not be governed by the protocol.

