14.2 Sample size, accrual rate and study duration

Study size is based on our primary objective of demonstrating that, compared to SIMRT, HTIMRT reduces the two year post treatment failure rate, by which we mean the proportion of patients with either biopsy failure or earlier evidence (within two years of treatment completion) of biochemical and/or clinical failure. (See definition in Section 9.1.) We expect the two-year failure rate in the standard fractionation arm to be 52.5%, representing the combined effect of a small rate of biochemical or clinical failure within two years, approximately 5%, and a relatively high rate of positive biopsy among the remaining 95% of patients, namely 50% ($0.05 + 0.95 \times 0.50 = 0.525$). This estimate is based on prior findings on randomized trials previously

organized by the PI. (75) Assuming equal allocation of patients to SIMRT and HTIMRT and sufficient follow-up to determine failure status at two years, a study size of 36 patients in each treatment arm provides 80% power to detect an absolute reduction of 30% in the two-year failure rate (biochemical, clinical, or biopsy), from 52.5% to 22.5%, using a one-sided Fisher's exact test with 5% significance level. To ensure a minimum of 72 study patients evaluable for the two year failure rate as our main study endpoint, we plan to enroll a total of 76 patients.

Based on an accrual rate averaging 2 patients per month, we plan to complete enrollment in 3.2 years. Patients will be followed for five years giving total study duration of 8.2 years. Analyses of some secondary endpoints, including acute toxicity, psychosocial parameters, biomarker distribution on ultrasound-guided biopsies, and initial MRI findings may be reported before the efficacy endpoints, including the primary endpoint. These secondary endpoints will be analyzed after all planned patients have been accrued, completed treatment and have a minimal potential follow-up of 3 months from the end of RT. The main efficacy endpoint requires less than five years follow up and will be performed after all patients have been assessed for two year post treatment failure status (2 yr. biopsy). Final efficacy analysis will be at the conclusion of study when patients have been followed for 5.25 years.

14.3 Definitions and endpoints:

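### No section requires the 2-year biopsy, which decides about 90% of expected control-arm failures, to be read without knowledge of treatment arm

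*Combined protocol and SAP*

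**What the plan says.** - **Open label.** Section 3.3.5 explains that the different number of fractions (40 v 38) "requires that the patients know their treatment". It goes on to limit which study data patients may see. It does not say what the pathologist or the urologist may know.
- **Reading.** Section 4.5 states: "Biopsies will be reviewed by a pathologist and the results (Gleason scoring and percent of tumor tissue) recorded in the patient's record per routine". Its title is general, but it sits in the pre-treatment workflow and does not name the 2-year biopsy. No other section gives a rule for reading.
- **Coding.** Section 4.5 also says that, for sections cut for biomarker analyses, "the slides will be labeled with a research ID number and will not contain patient information". It adds that the prostate database links the research ID to the medical record number and holds biopsy and treatment data.
- **Sampling at 2 years.** Sections 5.3 and 8.0 recommend 12-14 cores from named sites, at least 2-3 of them from suspicious or previously positive areas. They then allow a departure: "Fewer biopsies may be obtained at the discretion of the urologist". Section 3.3.4 allows ultrasound, fusion or MRI guidance for the endpoint biopsy and says that fusion finds substantially more positives.
- **Endpoint.** Section 9.1 counts positive biopsy findings without saying which pathology categories are positive. Section 14.5 lists four: negative, atypical, carcinoma with treatment effect, and carcinoma without it.
- **Design.** Section 14.2 assumes "a relatively high rate of positive biopsy among the remaining 95% of patients, namely 50" percent, and states that "a study size of 36 patients in each treatment arm provides 80% power" to detect a fall "from 52.5% to 22.5" percent, "using a one-sided Fisher's exact test with 5% significance level".

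**The concern.** In an open-label trial, the usual safeguard for an endpoint that needs judgement is to keep the assessor unaware of arm. Here that safeguard is not specified for the reading that decides most primary events. Section 8.0 itself notes that tumor cells showing radiation effect are often seen at 2-2.5 years, so borderline specimens are to be expected. A reader who knows that one arm received a boost to the dominant lesion could resolve such specimens differently by arm, in either direction and without intending to. With 36 patients per arm, a few reclassified specimens can change the result. Once the trial is reported, the objection could not easily be answered from the data.

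**Working it through.** **Inputs from section 14.2.** Early biochemical or clinical failure 5%; biopsy positivity 50% in the other 95%; SIMRT 52.5%, HTIMRT 22.5%; 36 per arm; one-sided Fisher's exact test at 5%.

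**Method.** Exact enumeration. For every pair of failure counts, reject if the hypergeometric tail probability is at most 0.05, then sum the product of the two binomial probabilities over the rejected pairs.

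**Step 1: the plan's own figure.** At 0.525 v 0.225, power is 80.3% with 36 per arm and 78.5% with 35. The stated design reproduces.

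**Step 2: weight of the biopsy.** 0.95 × 0.50 = 0.475, and 0.475 / 0.525 = 0.905. So about 90% of expected SIMRT failures are decided by the biopsy. In 36 patients this is 36 × 0.475 = 17.1 positive biopsies, and 10% of them is 1.7 patients.

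**Step 3: how few specimens matter.** Expected SIMRT failures are 36 × 0.525 = 18.9. With 19 failures on SIMRT, the test rejects at 11 or fewer on HTIMRT and not at 12.

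**Step 4: under-reading in one arm, no true effect.** Let a share g of positive biopsies in one arm be read as non-positive. That arm's observed rate is 0.05 + 0.475 × (1 − g), and the other stays at 0.525. The values of g are assumptions, because the documents give none.

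| g | Observed rate in the affected arm | Type I error, HTIMRT under-read | Type I error, SIMRT under-read |
|---|---|---|---|
| 0 | 52.5% | 3.8% | 3.8% |
| 5% | 50.1% | 5.8% | 2.4% |
| 10% | 47.75% | 8.5% | 1.5% |
| 20% | 43.0% | 16.7% | 0.5% |

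**Step 5: equal loss of sensitivity in both arms.** This could come, for example, from fewer cores. With sensitivity s, the rates are 0.05 + 0.475s and 0.05 + 0.175s. At s = 0.9 (47.75% v 20.75%) power is 72.4%; at s = 0.8 (43.0% v 19.0%) it is 63.5%. The cost is power. It does not favour either arm.

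**The case against.** Much of the case on the other side stands, and it limits the point. Four stronger readings are tempting.

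- **That the pathologist and urologist know the arm.** The documents do not say so, nor that the arm is visible to the reader. Masking is unspecified, and that is all that can be claimed.
- **That the endpoint biopsy is taken as routine care, with core number left to the urologist.** Sections 4.12 and 8.0 call it a research biopsy, and 5.3 and 8.0 recommend a 12-14 core template. Discretion extends only to taking fewer, although no minimum is given. The wording on up to 14 cores at the urologist's discretion in 3.3.4 concerns the pre-treatment biopsy.
- **That the plan already masks biomarker slides and merely leaves out the endpoint slides.** The research-ID labels are de-identification. They are not described as masking to arm, and the ID is linked to treatment data.
- **That the false-positive rate is inflated.** Nothing in the documents gives a direction. Under-reading in SIMRT lowers the type I error, and fewer cores taken equally in both arms costs power only.

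It can also be said that section 4.5 was written for pre-treatment tissue. That tissue is obtained before randomization, when there is no arm to know, and the items it records (Gleason score, percent tumor) are not the 14.5 categories. This is fair. But if 4.5 does not cover the 2-year biopsy, then no reading rule covers it, and the gap is wider.

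Finally, the result must reach the patient (5.3) and inform later management (8.0), so an identifiable report is needed. That calls for re-linkage after the reading. It does not require the arm to be known during it.

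**Conclusion.** The point holds as a gap in the plan: an open-label trial specifies no arm-masked reading for the judgement-based biopsy that supplies 47.5 of 52.5 expected control-arm failure points. No actual bias is shown, and neither the sample size nor the nominal power changes. The type I error range, from 0.5% to 16.7% around an unbiased 3.8%, is an illustration. It rests on assumed under-reading of 5% to 20% of positives in one arm, 52.5% true failure in both arms, and 36 evaluable patients per arm. The change is worth making because it is cheap and the primary result depends so heavily on this reading.

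**What to change.** State in sections 4.5, 5.3 and 8.0 that the existing pathologist assigns the 2-year biopsy to its 14.5 category with arm and dose plan withheld. Use a coded requisition or label, and re-link it once the reading is recorded so that the result still goes to the patient and the treating physician. The present research-ID label is not enough alone, because the database ties it to treatment; the reader must also have no access to that link while reading.

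Record the number of cores and the guidance platform for each 2-year biopsy, and report both by arm, so that any difference in sampling can be seen.

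Leave the urologist's discretion on core number as it is, and do not rely on masking the urologist, since patients know their arm and may disclose it.

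The cost is a small coding and re-linkage step and short additions to three sections. No extra reader, procedure or patient is needed.

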4.6 MRI and CT-Simulation

A second, limited prostate MRI study that includes T2w, T2*-weighted gradient echo sequence (T2-star for clear visualization of the gold markers (71)), and T1 sequences will be obtained at 2.0-2.5 mm cuts at least 1 week after fiducial marker placement, if applicable to facilitate fusion with CT-simulation images based on the markers. This limited MRI of the prostate will be fused to the original diagnostic MRI to ensure that the HTIMRT is accurately targeted to the center of the functional MRI-defined region.

CT-simulation will be obtained under the same conditions with typical pelvic immobilization. Images will be taken at 2.0 mm intervals from the top of the sacrum to 1 cm below the ischial tuberosities (to include the entire bladder and rectum). All patients will have tattoos placed at the anterior, right lateral, and left lateral isocenter skin points.

4.7 Risk Assessment for RT and ADT Planning

- *Favorable Risk:* Clinical and MRI T1-T2, Gleason 6, and PSA ≤ 10 . The biopsy information from the original diagnostic prostate biopsies will be used (not the information from the protocol prostate biopsies).
- *Intermediate Risk:* Clinical and MRI T1-T2, Gleason 7 or PSA >10 and ≤ 20 Patients are eligible for 4-6 (± 2 months) months of androgen deprivation therapy, starting up to 2 months prior to signing consent.
- *High Risk:* Palpitation T3a (with extraprostatic extension) or MRI<T3a or Gleason ≥ 8 or PSA >20 : These patients must be offered and refuse long term ADT. If the patient accepts long term ADT, they may not be enrolled on the study. They will be strongly

encouraged to receive 4-6 months of ADT, with 6 months preferred. However, ADT may be refused. ADT may begin up to 2 months prior to signing the consent.

4.8 GTV and CTV Contouring, PTV Definition and Planning Parameters

The CT and MRI simulation scans will be loaded into a planning computer and fused based on the fiducial markers, if applicable. The DCE-MRI will be fused to the MRI-simulation images. At each slice level, the pelvic bones, bladder, rectum, prostate, and proximal seminal vesicles will be outlined based primarily on CT, but with MRI consideration.

The **Gross Tumor Volume** (GTV) region will consist of the early DCE-MRI enhancing regions, except for anterior regions. If an anterior region enhances early, is associated with water restriction on DWI and/or elevated choline + creatinine metabolites on MRS, these regions should be included in the GTV. The GTV will be shaped such that the posterior edge is ≥ 2 mm from the rectum to avoid excessive dose to the rectum. The Clinical Target Volume (CTV) will include the prostate (with GTV) and the proximal seminal vesicles (usually 7-10 mm and/or $\leq 50\%$ of length, whichever is shorter). The CTV may include an extra 1-2 mm beyond the GTV in regions of known bulky disease and/or extracapsular extension as determined by the diagnostic biopsy information and/or MRI. The Planning Target Volume (PTV), will be 3-5 mm around the CTV in all dimensions. For tumors at the base, a margin of 5 mm on the proximal seminal vesicles is recommended.

- Arm I, SIMRT: At least 95% of the PTV should receive 80 Gy in 40 fractions, at 2.0 Gy per fraction. The maximum dose to the PTV should be $<115\%$ of the prescription dose.
- Arm II, HTIMRT: The dose to the GTV will be escalated by dose painting to 2.35 Gy per fraction. The HT boost region will receive an absolute dose of 89.3 Gy. Assuming an α/β ratio of 3.0, this would be equivalent to 95.5 Gy in 2.0 Gy fractions. The GTV region will be shaped such that the posterior edge is ≥ 2 mm from the rectum to avoid excessive dose to the rectum. The maximum dose to the rectum per day should not exceed 2.25 Gy. The normal tissue constraints are otherwise the same as for Arm I. The CTV volume is the same as for Arm I; at least 95% of the PTV should receive 76 Gy in 38 fractions, at 2.0 Gy per fraction. The maximum dose heterogeneity in PTV1 will be affected substantially by GTV (the area of the HT boost). High dose gradients are acceptable as long as the normal tissue constraints are met.

